### 8.4.4 Regulatory Reporting Requirements for SAE

08V5WO

Prompt notification (within 24 hours) by the investigator to the Sponsor of SAE is essential so that legal obligations and ethical responsibilities toward the safety of participants and the safety of a study intervention under clinical investigation are met.

The Sponsor has a legal responsibility to notify both the local regulatory authority and other regulatory agencies about the safety of a study intervention under clinical investigation. The Sponsor will comply with country-specific regulatory requirements and global laws and regulations relating to safety reporting to regulatory authorities, IRB/IECs, and investigators.

Investigator safety reports must be prepared for SUSARs according to local regulatory requirements and Sponsor policy and forwarded to investigators as necessary.

An investigator who receives an investigator safety report describing an SAE or other specific safety information (eg, summary or listing of SAEs) from the Sponsor will file it along with the IB and will notify the IRB/IEC, if appropriate according to local requirements.

#### 8.4.5 Pregnancy and Exposure During Breastfeeding

Although pregnancy and infant exposure during breastfeeding are not considered AEs, any pregnancy or infant exposure during breastfeeding in a participant (spontaneously reported to the investigator or their designee) that occurs during the study are reportable to the Sponsor.

All reported pregnancies must be followed to the completion/termination of the pregnancy.

Any pregnancy complication will be reported as an AE or SAE.

The medical reason (example: maternal health or fetal disease) for an elective termination of a pregnancy will be reported as an AE or SAE. Prenatal testing showing fetus will be born with severe abnormalities/congenital anomalies that leads to an elective termination of a pregnancy will be reported as an SAE for the fetus.

Pregnancy outcomes of ectopic pregnancy, spontaneous abortion, missed abortion, benign hydatidiform mole, blighted ovum, fetal death, intrauterine death, miscarriage, and stillbirth must be reported as serious events (Important Medical Events). If the pregnancy continues to term, the outcome (health of infant) must also be reported.

# 8.4.6 Disease-related Events and/or Disease-related Outcomes Not Qualifying as AEs or SAEs

Not applicable.

#### **8.4.7** Events of Clinical Interest

Selected serious and nonserious AEs are also known as ECIs and must be reported to the Sponsor.

Events of clinical interest for this study include:

- 1. An overdose of Sponsor's product, as defined in Section 8.5.
- 2. Potential DILI events defined as an elevated AST or ALT laboratory value that is greater than or equal to 3× the ULN and an elevated total bilirubin laboratory value that is greater than or equal to 2× the ULN and, at the same time, an alkaline phosphatase laboratory value that is less than 2× the ULN, as determined by way of protocol-specified laboratory testing or unscheduled laboratory testing.\*
  - \*Note: These criteria are based on available regulatory guidance documents. The purpose of the criteria is to specify a threshold of abnormal hepatic tests that may require an additional evaluation for an underlying etiology. The study-site guidance for assessment and follow-up of these criteria can be found in the Investigator Study File Binder (or equivalent).

It may also be appropriate to conduct additional evaluation for an underlying etiology in the setting of abnormalities of liver blood tests including AST, ALT, bilirubin, and alkaline phosphatase that do not meet the criteria noted above. In these cases, the decision to proceed with additional evaluation will be made through consultation between the study investigators and the Sponsor Clinical Director. However, abnormalities of liver blood tests that do not meet the criteria noted above are not ECIs for this study.

#### **8.5** Treatment of Overdose

For purposes of this study, an overdose will be defined as any dose of any drug administered as part of the study exceeding the dose prescribed by the protocol. It is up to the investigator or the reporting physician to decide whether a dose is to be considered an overdose, in consultation with the Sponsor.

Sponsor does not recommend specific treatment for an overdose. Decisions regarding dose interruptions or modifications will be made by the investigator in consultation with the Sponsor Clinical Director based on the clinical evaluation of the participant.

#### 8.6 Pharmacokinetics

The decision as to which plasma and/or urine samples collected will be measured for evaluation of PK/pharmacodynamics will be collaboratively determined by the Sponsor (eg, samples at lower doses may not be measured if samples at higher doses reveal undetectable drug concentrations). If indicated, these samples may also be measured and/or pooled for assay in an exploratory manner for metabolites and/or additional pharmacodynamic markers. Blood samples collected may be stored and further analysis may be performed, if required.

#### 8.6.1 Blood Collection for Plasma MK-2060

Sample collection, storage, and shipment instructions for plasma samples will be provided in the Study Operations Manual by the Sponsor.

#### 8.7 Pharmacodynamics

Sample collection, storage, and shipment instructions for pharmacodynamic samples will be provided in the Study Operations Manual. Blood samples collected may be stored and further analysis may be performed, if required.

#### 8.7.1 Blood Collection for PT, aPTT, FXI Activity

PT and aPTT at screening, predose, and postdose specified in the SoA will be performed locally for safety monitoring. All other predose and postdose PT and aPTT, as well as FXI activity will be performed at a central vendor for analysis. Sample collection, storage, and shipment instructions for the PT, aPTT, FXI activity will be provided in a separate Study Operations Manual by the Sponsor. The primary data for statistical analysis and modeling will be based on the information from the central vendor.

#### 8.7.2 Blood for Plasma ADA

Sample collection, storage, and shipment instructions for plasma samples will be provided in a separate Study Operations Manual by the Sponsor.

#### 8.8 Biomarkers

Collection of samples for other biomarker research is also part of this study. The following samples for biomarker research are required and will be collected from all participants as specified in the SoA.

• Blood for genetic analysis

#### 8.8.1 Planned Genetic Analysis Sample Collection

The planned genetic analysis sample should be drawn for planned analysis of the association between genetic variants in DNA and drug response. This sample will not be collected at the site if there is either a local law or regulation prohibiting collection, or if the IRB/IEC does not approve the collection of the sample for these purposes. If the sample is collected, leftover extracted DNA will be stored for FBR if the participant provides documented informed consent for FBR. If the planned genetic analysis is not approved, but FBR is approved and consent is given, this sample will be collected for the purpose of FBR.

Sample collection, storage, and shipment instructions for planned genetic analysis samples will be in the Operations/Laboratory Manual.

#### 8.9 Future Biomedical Research Sample Collection

If the participant provides documented informed consent for FBR, the following specimens will be obtained as part of FBR:

• Leftover samples from Section 8.8.

### 8.10 Health Economics Medical Resource Utilization and Health Economics

Health Economics are not evaluated in this study.

#### **8.11** Visit Requirements

Visit requirements are outlined in Section 1.3. Specific procedure-related details are provided in Section 8.

#### 8.11.1 Screening

08V5WO

Approximately 4 weeks before intervention randomization, potential participants will be evaluated to determine that they fulfill the entry requirements as set forth in Section 5.

Participants may be rescreened after consultation with the Sponsor. Rescreening should include all screening procedures listed in the SoA, including consent review. Rescreen procedures cannot be conducted the day prior to intervention randomization if there are Day -1 procedures planned per protocol.

#### **8.11.2** Treatment Period

Refer to the Schedule of Activities (Section 1.3) and Administrative and General Procedures (Section 8.1).

After all predose procedures have been completed and it is confirmed that the participant meets eligibility; the participant will be given a participant ID bracelet and assigned a unique randomization number associated with a specific treatment as defined by a computer-generated randomization schedule. Participants will report to the CRU prior to the scheduled day of dosing or time specified by the investigator. On the day of dosing, participants will fast from all food and drinks, except water, for at least 8 hours prior to until 2-hours poststudy drug administration when they will be given a light breakfast (see Section 5.3.1). Participants will be administered study intervention as indicated in Section 6. Participants who, on Day 1, have a significant acute illness or fever prior to the administration of study drug may be rescheduled.

#### 8.11.3 Poststudy

Participants will be required to return to clinic approximately 90 days for Part 1, 130 days for Part 2, and 120 days for Part 3 after the last dose of study intervention for the poststudy visit. If the poststudy visit occurs fewer than 90/130/120 days after the last dose of study intervention, a subsequent follow-up telephone call should be made at 90/130/120 days post the last dose of study intervention to determine if any AEs have occurred since the poststudy clinic visit.

# 8.11.4 Participants Discontinued From Study Intervention but Continuing to be Monitored in the Study

At any point if a participant discontinues from treatment but continues to be monitored in the study, all study procedures specified in the SoA may be completed at the discretion of the investigator and with Sponsor agreement. The subset of study procedures completed will be communicated in a PCL.

CKD4 and CKD5 participants who experience disease progression and convert to ESKD on HD following administration of study intervention but prior to the post-study visit may continue to be monitored in the study per the visit requirements in the SoA.

#### 8.11.5 Safety Phone Call Follow-Up

A safety follow-up phone call will be performed approximately 14 days after the poststudy visit (within the visit windows allowed per protocol). The safety follow-up phone call must be performed by appropriately trained study site staff. At the discretion of the investigator an in-person follow-up may be performed. If the initial call is unsuccessful, the study site should

make a total of 3 attempts. All attempts to contact the participants will be recorded in the source documents. The calls will facilitate the collection of relevant safety information. The participant will be interviewed to obtain information relating to AEs and SAEs. All safety information described by the participant must be documented in the source documents.

#### 8.11.6 Critical Procedures Based on Study Objectives: Timing of Procedure

For this study, the blood sample for MK-2060 is the critical procedure.

At any post-dose time point, the blood sample for MK-2060 needs to be collected as close to the exact time point as possible. All other procedures should be completed as close to the prescribed/scheduled time as possible. Study procedures can be performed before or after the prescribed/scheduled time.

The order of priority can be changed during the study with joint agreement of the investigator and the Sponsor Clinical Director.

Any nonscheduled procedures required for urgent evaluation of safety concerns take precedence over all routine scheduled procedures.

The following variance in procedure collection times will be permitted.

- Screening 2 procedures: up to additional 4 hours of scheduled time
- PK, Pharmacodynamic and Safety Collection as outlined in Table 7, Table 8, and Table 9.

Table 7 Pharmacokinetic, Pharmacodynamic and Safety (Blood/Urine) Collection Windows for Part1

Pharmacokinetic, Pharmacodynamic, Safety Collection	Pharmacokinetic, Pharmacodynamic Safety Collection Window		
0 to < 4 hours	5 min		
4 - < 8 hours	15 min		
8 - < 24 hours	30 min		
24 hours - < 48 hours	60 min		
48 hours - < 120 hours	2 hours		
120 hours - ≤ 168 hours	24 hours		
Day 11 + Day 14	1 Day		
Day 21	2 Days		
Day 28	3 Days		
Day 60 + Day 90	5 Days		

Table 8 Pharmacokinetic, Pharmacodynamic and Safety (Blood/Urine) Collection Windows for Part 2

Pharmacokinetic, Pharmacodynamic, Safety Collection	Pharmacokinetic, Pharmacodynamic, Safety Collection Window		
0 to < 4 hours	5 min		
Days 1, 2, 3, 4, 8, 15, 22, 23, and 29	No flexible window for the scheduled day		
Days 10 and 17	±1 Day		
Day 26	+1 Day		
Days 35, 42, 49 and 63	±2 Days		
Days 81 and 111	±3 Days		
Day 130	±7 Days		

Table 9 Pharmacokinetic, Pharmacodynamic and Safety (Blood/Urine) Collection Windows for Part 3

Pharmacokinetic, Pharmacodynamic, Safety Collection	Pharmacokinetic, Pharmacodynamic, Safety Collection Window		
0 to < 4 hours	5 min		
4 - < 8 hours	15 min		
8 - < 24 hours	30 min		
24 hours - < 48 hours	60 min		
48 hours - < 120 hours	2 hours		
120 hours - ≤ 168 hours	24 hours		
Day 11 + Day 14	1 Day		
Day 21	2 Days		
Day 28	3 Days		
Day 60 + Day 90 + Day 120	5 Days		

- Part 1, 2, and 3 Day 1 predose standard safety evaluations: VS and ECG at 3 hours; laboratory safety tests and physical exam at 24 hours
- Part 2 Days 8, 15, and 22 predose standard safety evaluations: VS, ECG, and laboratory safety tests at 3 hours.
- Post-dose standard safety evaluations: VS, ECG, laboratory safety tests, and physical exam
  - Prior to 24-hours postdose may be obtained within 15 minutes of the theoretical sampling time
  - Between 24-hours and <48-hours postdose may be obtained within 1 hour of the theoretical sampling time
  - From 48-hours to <120-hours postdose may be obtained within 2 hours of the theoretical sampling time

Note: Visit windows defined by +/- X day(s) refers to calendar days.

## 8.11.7 Study Design/Dosing/Procedures Modifications Permitted Within Protocol Parameters

This is a Phase 1 assessment of MK-2060 in humans, and the PK, pharmacodynamic, and safety profiles of the compound are still being elucidated. This protocol is written with some flexibility to accommodate the inherent dynamic nature of Phase 1 clinical studies. Modifications to the dose, dosing regimen, and/or clinical or laboratory procedures currently outlined may be required to achieve the scientific goals of the study objectives and/or to ensure appropriate safety monitoring of the study participants.

As such, some alterations from the currently outlined dose and/or dosing regimen may be permitted based on newly available data, but the maximum daily dose may not exceed those currently outlined in the protocol.

- Repeat of or decrease in the dose of the study intervention administered in any given period/panel/part
- Addition of study pause
- Instructions to take study intervention with or without food or drink may also be modified based on newly available data
- Modification of the PK/pharmacodynamic sample processing and shipping details based on newly available data

The PK/pharmacodynamic sampling scheme currently outlined in the protocol may be modified during the study based on newly available PK or pharmacodynamic data (e.g., to obtain data closer to the time of peak plasma concentrations). If indicated, these collected samples may also be assayed in an exploratory manner for metabolites and/or additional pharmacodynamic markers.

Up to additional 50 mL of blood may be drawn for safety, PK, and/or pharmacodynamic analyses. The total blood volume withdrawn from any single participant will not exceed the maximum allowable volume during his/her participation in the entire study (Appendix 8).

The timing of procedures for assessment of safety procedures (eg, VS, ECG, safety laboratory tests, etc.) may be modified during the study based on newly available data. Additional laboratory safety tests may be added to blood samples previously drawn to obtain additional safety information. These changes will not increase the number of study procedures for a given participant during his/her participation in the entire study.

It is understood that the current study may use some or none of the alterations described above. Any alteration made to this protocol to meet the study objectives must be detailed by the Sponsor in a letter to the Study File and forwarded to the investigator for retention. The letter may be forwarded to the IRB/IEC at the discretion of the investigator.

#### 9 STATISTICAL ANALYSIS PLAN

#### 9.1 Statistical Analysis Plan Summary

This section contains a brief summary of the statistical analyses for this study. Full details can be found in the subsequent sections.

#### Safety

Summary statistics and plots will be generated for raw laboratory safety tests, ECGs, and/or VS as well as for change from baseline, as deemed clinically appropriate. Depending on the safety parameter, the difference from baseline will either be computed on the original scale (raw change from baseline) or on the log scale and back-transformed for reporting (percent change from baseline).

#### 9.2 Responsibility for Analyses

The statistical analysis of the data obtained from this study will be conducted by, or under the direct auspices of, the Early Clinical Development Statistics Department in collaboration with the Quantitative Pharmacology and Pharmacometrics Department and Translational Pharmacology Department of the Sponsor.

If, after the study has begun, changes are made to the statistical analysis plan stated below, then these deviations to the plan will be listed, along with an explanation as to why they occurred, in the Clinical Study Report.

#### 9.3 Hypotheses/Estimation

Objectives of the study are stated in Section 3.

#### 9.4 Analysis Endpoints

#### **Primary Endpoints**

- 1. Primary endpoints are bleeding related AEs, AEs, and discontinuations due to AEs.
- Pharmacokinetics: The pharmacokinetic variables of primary interest for MK-2060 are measurement of MK-2060 plasma AUC0-∞, AUC0-168, Cmax, C168, Tmax, terminal t1/2, CL/F and Vz/F

#### Part 1 Hypothesis:

The true geometric mean AUC0-∞ is at least 11300 nM\*hr. This value is based on the preliminary modeling and simulation analyses using data form MK-2060 P001 and MK-2060 P004.

PROTOCOL/AMENDMENT NO.: 011-01

#### Secondary Endpoints

2. Pharmacodynamics: The pharmacodynamics variable of secondary interest is fold-change in baseline in aPTT values. Baseline is defined as the predose value.

#### **Exploratory Endpoints:**

Pharmacodynamics: The pharmacodynamics variables of exploratory interest are Factor XI activity levels and prothrombin time.

### 9.5 Analysis Populations

The following populations are defined for the analysis and reporting of data. All participants will be reported, and their data analyzed, according to the treatment(s) they actually received.

*All Participants as Treated:* The All Participants as Treated Population consists of all participants who received at least one dose of treatment. This population will be used for assessments of safety and tolerability.

Per-Protocol (PP): The Per-Protocol Population consists of the set of data generated by the subset of participants who comply with the protocol sufficiently to ensure that these data will be likely to exhibit the effects of treatment, according to the underlying scientific model. Compliance covers such considerations as exposure to treatment, availability of measurements and absence of important protocol deviations. Important protocol deviations will be identified to the extent possible prior to unblinding by individuals responsible for data collection/compliance, and its analysis and interpretation. Any participants or data values excluded from analysis will be identified, along with their reason for exclusion, in the CSR. At the end of the study, all participants who are compliant with the study procedure as aforementioned and have available data from at least one treatment will be included in the Per-Protocol dataset.

#### 9.6 Statistical Methods

Summary statistics and plots will be generated for raw laboratory safety tests, ECGs, and/or VS as well as for change from baseline, as deemed clinically appropriate. For all endpoints descriptive summary will be provided. For categorical measurements, counts and percentage numbers will be provided. Similarly, for continuous measurements, mean, standard deviation, median, min, max will be provided. Depending on the safety parameter, the difference from baseline will either be computed on the original scale (raw change from baseline) or on the log scale and back-transformed for reporting (percent change from baseline) as appropriate. Values will be listed for each PK parameter (including Tmax and apparent terminal t1/2), and appropriate non-model based descriptive statistics will be provided: N (number of participants with non-missing data), arithmetic mean, standard deviation, arithmetic percent CV (calculated as 100\*sqrt(exp(s2)-1), where s2 is the observed variance on the natural log-scale.)

PRODUCT: MK-2060 PROTOCOL/AMENDMENT NO.: 011-01

Descriptive statistics as well as appropriate plots will be displayed for aPTT fold change from baseline. Similar statistics will be provided for the fold changes in the exploratory endpoints such as PT and FXI activity levels.

To test the part 1 primary hypothesis, the posterior probability that the true geometric mean of AUC0-∞ after a single well-tolerated dose of MK-2060 in adult participants with CKD4 is at least 11345 nM\*hr, will be calculated using a noninformative prior. The CV for AUC0-∞ is expected to be approximately 30% (assuming similar variability as in MK-2060 P004). If this posterior probability exceeds 60%, then the primary research hypothesis will be supported.

Since Part 2 and Part 3 involves estimation, descriptive statistics (mean, median, standard deviation, min, max values) will be provided for primary and secondary endpoints.

#### 9.7 Interim Analyses

No interim analysis is planned for this study.

#### 9.8 Multiplicity

Since there is a single prespecified primary hypotheses, no adjustments for multiplicity are needed.

#### 9.9 Sample Size and Power Calculations

For Part 1, approximately 12 participants will be enrolled for this study. Participants will be randomized in a 3:1 ratio to receive a single 30-mg SC dose of MK-2060 (n=9) or placebo (n=3).

Thus, with all 9 participants in MK-2060 group completing the study and a posterior probability threshold of 60%, there is approximately 82% probability of supporting the primary hypothesis if the true geometric mean of AUC0- $\infty$  is 12800 assuming CV=30% and natural log-normal distribution for AUC0- $\infty$ . We assume that at 30-mg dose SC dose, the true GM is 12800. A table with PP calculations with assumptions about various values of the true GM and with CV=30% is as follows:

True Geometric Mean	Probability of Go (%)
12500	75.6%
12600	77.9%
12700	80.3%
12800	82.4%
12900	84.4%
13000	86.2%

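### The Section 9.9 probability-of-Go table names no target and does not reproduce to its printed precision at either documented target (11300 or 11345); the gap is small and conservative

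*Combined protocol and SAP*

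**What the plan says.** Section 9.4 gives the Part 1 hypothesis as "The true geometric mean AUC0-∞ is at least 11300" nM*hr, and Sections 1.1 and 3 use the same value. Section 9.6, which describes the test, computes the posterior probability that the geometric mean "is at least 11345" nM*hr. That probability "will be calculated using a noninformative prior", and the decision rule is: "If this posterior probability exceeds 60%, then the primary research hypothesis will be supported".

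Section 9.9 bases its calculation on "with all 9 participants in MK-2060 group completing the study and a posterior probability threshold of 60"%, "assuming CV=30% and natural log-normal distribution" for AUC0-∞. It takes 12800 as the true geometric mean and concludes that "there is approximately 82% probability of supporting the primary hypothesis". Its table runs from 12500 to 13000 in steps of 100 and prints 75.6, 77.9, 80.3, 82.4, 84.4 and 86.2%. Section 9.9 does not state the target, the log-scale SD, whether that SD is treated as known, or whether the figures were calculated or simulated.

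**The concern.** The table and its headline are the only quantitative support for nine active participants in Part 1. With these inputs the probability of meeting the rule has a closed form, so a reader should be able to recover values printed to 0.1 point. At neither documented target is that possible, and the difference has the same sign in every row.

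What is at stake is traceability. A reader cannot tell which version of the rule the 82% describes. Reconciling 11300 with 11345 in the text alone would still leave a table that matches neither.

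**Working it through.** **Inputs.** n = 9 active, all completing (9.9); threshold 0.60 (9.6, 9.9); noninformative prior (9.6); CV 30%, log-normal (9.9); true geometric mean GM from 12500 to 13000 (9.9); target T = 11300 (1.1, 3, 9.4) or 11345 (9.6).

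**Log-scale SD.** Section 9.6 defines the CV of PK parameters as sqrt(exp(s²) − 1). Inverting this for 30% gives σ = sqrt(ln 1.09) = 0.2936. Section 9.9 does not state the conversion, so σ = 0.30 is checked as an alternative reading.

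**Rule, SD unknown.** With the usual noninformative prior, the posterior probability exceeds 0.60 when √9 × (mean log AUC − ln T)/s > t(0.60; 8 df) = 0.262. The left side follows a noncentral t distribution with 8 df and noncentrality δ = 3 × ln(GM/T)/σ.

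**Rule, SD known.** P(Go) = Φ(δ − z), with z = 0.2533 at 0.60.

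**At GM = 12800, σ = 0.2936:**
- T = 11300: ln(12800/11300) = 0.1246; δ = 1.274; Φ(1.274 − 0.253) = 84.6%. The noncentral t also gives 84.6%.
- T = 11345: ln(12800/11345) = 0.1207; δ = 1.233; Φ(1.233 − 0.253) = 83.6%. The noncentral t also gives 83.6%.

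With σ = 0.30 the two values are 84.0% and 83.0% (known SD), or 83.9% and 82.9% (noncentral t).

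**All rows, noncentral t, σ = 0.2936 (%):**

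| True GM | Printed | T = 11300 | Gap | T = 11345 | Gap |
|---|---|---|---|---|---|
| 12500 | 75.6 | 78.1 | 2.5 | 76.9 | 1.3 |
| 12600 | 77.9 | 80.4 | 2.5 | 79.3 | 1.4 |
| 12700 | 80.3 | 82.6 | 2.3 | 81.5 | 1.2 |
| 12800 | 82.4 | 84.6 | 2.2 | 83.6 | 1.2 |
| 12900 | 84.4 | 86.4 | 2.0 | 85.5 | 1.1 |
| 13000 | 86.2 | 88.0 | 1.8 | 87.2 | 1.0 |

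Treating the SD as known moves these values by about 0.1 point. With σ = 0.30 the gaps shrink to 1.2 to 1.9 points at 11300 and 0.4 to 0.8 at 11345, and every printed row is still the lower figure.

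**What would give the printed table?** Several settings come close, and each departs from something the plan states:
- n = 9, σ = 0.2936, T = 11400: within 0.2 point. No section gives this target.
- n = 9, σ = 0.30, T about 11370: within about 0.1 point. No section gives this target either.
- n = 8, σ = 0.30, T = 11300 (known SD): 75.7, 78.0, 80.2, 82.2, 84.0, 85.7; within 0.5 point, but 9.9 uses nine.
- n = 9, σ = 0.30, T = 11345, threshold 0.61 (known SD): within 0.2 point, but the threshold is 0.60.

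**The case against.** The case for leaving the table alone is that the discrepancy is small and nothing turns on it. At 11345, the value in the operative test, every row is within 1.5 points, and within 0.8 if CV 30% is read as a log-SD of 0.30; 83.0% is not far from a figure described as approximate. The decision rule in 9.6 does not use the table. Sections 4.2 and 4.3 report that preliminary Part 1 data already support the Part 2 regimen, so a prospective probability that moves by one or two points changes no decision. Settling the target would in any case require a new table.

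Most of this stands, and it fixes the grade as minor. It does not make the table right. Adjacent printed rows differ by only 1.8 to 2.4 points, so a tolerance of about 2 points is nearly a whole row: at 11300, the computed value for 12700 (82.6%) would pass for the printed value at 12800 (82.4%). The CV formula in 9.6 also favours 0.2936 over 0.30. Independent simulation error would scatter in both directions. Draws shared between rows could shift them together, but the plan does not mention simulation.

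A reader might infer from the close fit at 11400 that the sponsor used that target, and that the 82% belongs to a rule outside the plan. The documents do not support this. Changing the sample size, the log-SD or the threshold instead fits nearly as well, so the printed numbers do not identify the input that differed.

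**Conclusion.** The point holds as a minor error of calculation or reporting. With the plan's inputs and its own CV formula, the headline should be 84.6% at 11300 or 83.6% at 11345, against 82.4% printed. This rests on nine evaluable active participants, log-normal AUC and a standard noninformative prior; whether the SD is treated as known hardly matters.

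A reader might also conclude that the sample size is unsupported. It is not: at either target, and under either reading of the CV, the recalculated probability is higher than the one claimed. The defect that matters more is that 9.9 names no target while 9.4 and 9.6 disagree.

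**What to change.** 1. Choose one target and use it in Sections 1.1, 3, 9.4 and 9.6.
2. In 9.9, state that target, the log-SD (0.2936 if CV 30% is converted by the 9.6 formula), whether the SD is treated as known or unknown, and whether the figures are closed-form or simulated.
3. Regenerate the table and headline. If 11300 is kept, use the 11300 column above and a headline of about 85%; if 11345 is kept, use the 11345 column and about 84%. Both columns assume log-SD 0.2936 and the noncentral t with 8 df.
4. If the printed values came from another input, state it and justify it instead.

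The cost is one reconciled target, six numbers and a sentence or two in 9.9. Sample size, conduct and the 60% threshold do not change.
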